Although risk calculators can improve comprehension and produce favorable changes in health cognitions that lead to behavior change (e.g., accuracy of perceived risk, response efficacy, intentions), the effect of calculators on behavior itself is modest.^[2-4] However, the gap between intentions and behavior can be bridged via interventions that help people develop self-regulatory skills, such as developing action plans for how to achieve each step of the behavior.^[5-8] Mental imagery may be particularly useful in the development and realization of these plans.^[5, 9, 10]

We will adapt an existing and effective mental imagery-based self-regulation physical activity intervention^[5] for incorporation into the working risk calculator and compare its effectiveness in increasing physical activity behavior to an active control that addresses sleep hygiene.

RISK CALCULATOR AND MENTAL IMAGERY (Conceptual Model)

The conceptual model was adapted from the Health Action Process Approach (HAPA).^[8] It asserts that behavior change occurs in two phases. The **motivation phase** is most relevant for people who do not engage in the recommended behavior. The goal of interventions that target the motivation phase – such as the risk calculator – is to increase intentions to engage in the behavior. Risk perceptions are important in this phase because they raise awareness of the consequences of not engaging in the behavior. Together with outcome expectancies (e.g., the expected consequences of engaging in the behavior, operationalized here as response efficacy), perceived severity of the health outcome, and action self-efficacy (i.e., confidence in one's ability to initiate a new behavior), risk perceptions influence intentions to start the behavior change process. Note that the risk calculator is not expected to increase action self-efficacy or perceived severity because it was not designed with a component to target those constructs.

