In addition, we will also recruit participants in person at various locations around St. Louis. The locations will be determined by the REC and will include publicly available places with private space available, like laundromats, libraries, and community centers. In this case, research assistants will speak with potential participants in person to assess interest in the study. If potential participants are interested in participating in the study, research assistants will go through appendix H, the eligibility screener. If the participant is eligible, the study team member will record the participant's contact information on Appendix I, the Contact Info Sheet. If the participant is able to conduct the data collection session immediately, the research assistant will continue on to begin the data collection session following Appendix W (Aim 2 Data collection session 1 guide). If the participant is not able to conduct the data collection session immediately, we will schedule a time for the session at a later date, or offer times for walk-in sessions. Study coordinators will schedule sessions to take place either at the Taylor Avenue Building (Wash U) or at a mutually agreed upon public place with adequate private space to conduct the interview (e.g. a meeting room at a library). When the participant arrives for the session, the research assistant will explain the study procedures, obtain written consent, and begin data collection.

We will enroll 500 participants. Recruitment will be stratified based on race (at least 50% racial/ethnic minority) and education (at least 50% will have no college experience) to ensure adequate representation of populations that experience health disparities and, consequently, to increase relevance of the intervention to those groups.

Research Plan

RISK CALCULATOR AND MENTAL IMAGERY

Design

This study will use a 3 (risk presentation condition: text vs. table vs. risk ladder) x 2 (mental imagery condition: physical activity vs. sleep hygiene) experimental design. Participants will be block randomized to ensure that each of the 6 experimental conditions has equal numbers of participants at the end of the study. Randomization will occur by the computer program after eligibility screening and consent, but prior to engaging in any study activities.

Blinding

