All hypotheses and research questions will be examined using separate analyses for each outcome variable. Assumptions of each type of test will be checked (e.g., assumptions of normality and homogeneity of variance for ANOVAs). If there are violations, non-parametric tests will be used instead. Sex will be a covariate because there are no valid prediction models for male breast cancer, so men will not be shown a breast cancer risk estimate. The inclusion of other personal characteristics as covariates will be determined by the results of the preliminary analyses. Tests of moderation will be conducted by creating interaction terms between the risk presentation condition or mental imagery condition variables, as appropriate, and the variable assessing the moderator of interest. All statistical tests will be based on list-wise deletion except structural equation models, which can accommodate missing data.

Mediation analyses will be conducted using structural equation modeling (SEM). Full Information Maximum Likelihood estimation (FIML)^[44] will be used to allow the inclusion of missing data. Standardized estimates will be calculated and bias-corrected bootstrapping will be used to obtain the 95% confidence intervals.^[45-48] Criteria assessing model fit will also be examined (e.g., Standardized Root Mean Square Residual $\leq .08$, comparative fit index $\geq .95$, root mean square error of approximation $\leq .06$).^[49, 50] Mediation analyses will examine each construct as an individual mediator first, and then as a multiple mediator model.

Table 2 below describes the analyses that will be conducted for each hypothesis or research question.

Table 2. Overview of Statistical Analyses

	Priority	Statistical test(s)	Outcomes	Predictors/Mediators/Moderators
Risk Calculator				
H1; RQ1	Primary	3 arm ANOVA, 2 planned contrasts (risk ladder vs. text; risk ladder vs. table)	Comprehension, intentions	Predictor: Risk presentation condition
H2	Secondary	SEM	Intentions	Predictor: Risk presentation condition (risk ladder vs. text) Mediators: comprehension, risk perceptions, response efficacy, worry, affective reactions to information, affective attitudes to exercise, anticipated regret
H3	Secondary	3 arm ANOVA, planned contrast (risk ladder vs. text)	Change in physical activity (mins/week at 90 days – mins/week at baseline)	Predictor: Risk presentation condition

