H4	Secondary	SEM	Change in physical activity (mins/week at 90 days – mins/week at baseline)	Predictor: Risk presentation condition (risk ladder vs. text) Mediator: Intentions
RQ2	Secondary	3 arm ANOVA, planned contrast (risk ladder vs.	Risk perceptions, response efficacy, worry, affective reactions to information, affective attitudes	Predictor: Risk presentation condition

table) to exercise, anticipated regret

RQ3 Secondary 3 arm ANOVA Comprehension, intentions Predictor: Risk presentation condition
Moderators: Education, race/ethnicity, numeracy, health and graph literacy

Mental Imagery

H5	Primary	T-test	Change in physical activity (mins/week at 90 days – mins/week at baseline)	Predictor: Mental imagery condition
RQ5	Primary	ANOVA	Change in physical activity (mins/week at 90 days – mins/week at baseline)	Predictor: Mental imagery condition Moderators: Education, race/ethnicity, numeracy, health and graph literacy
H6	Secondary	Regression (physical activity mental imagery condition only)	Change in physical activity (mins/week at 90 days – mins/week at baseline)	Predictors: Week 4 action planning, coping planning, action self-efficacy, maintenance self-efficacy, recovery self-efficacy, affective attitudes to exercise, perceived vividness
RQ6	Secondary	Regression (physical activity mental imagery condition only)	Weekly change in minutes of physical activity, assessed by 4 difference scores: Week1-Baseline; Week2-Week1; Week3-Week2; and Week4-Week3	Predictors: For each weekly behavioral assessment, use the previous week's measures of the following constructs: action planning, coping planning, action self-efficacy, maintenance self-efficacy, recovery self-efficacy, affective attitudes to exercise, perceived vividness.

Sample Size Calculations

We will enroll 500 participants at baseline. This will enable us to test the primary hypothesis for each of the components of the study. This calculation was based on the information below.

RISK CALCULATOR

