Sample size was calculated to be able to detect an effect of risk presentation strategy on the primary outcome variables comprehension and intentions (Risk Calculator Hypothesis 1 and RQ1). Based on a 2-sided test of means for 3 groups (ANOVA) at 80% power, $\alpha=.05$, $df=2$, and Cohen's f effect size of 0.15 (approximately equivalent to Cohen's d of 0.3),^[51, 52] we anticipate needing 432 participants. The effect size estimate was based on a study of personalized breast cancer risk and risk reduction communication that found an effect on intentions to increase physical activity of approximately $f=0.25$ and an effect on response efficacy of approximately $f=0.20$.^[4] However, most of those participants were white, highly educated, had high health literacy, and recruited from a breast health center. Thus, we can expect the findings in our more diverse sample to be somewhat lower. We chose $f=.15$ as a reasonable compromise because it represents slightly more than a minimal effect,^[53] but is also logistically feasible. To account for the possibility of 10% missing data in Baseline Survey 1, which assesses the constructs for the Risk Calculator Hypothesis 1, we would need to enroll 480 participants to obtain 432 completed surveys.

MENTAL IMAGERY

[name] prior self-regulatory intervention accounted for approximately 20% of the unique variance in physical activity at 4-week follow-up.^[5] This is approximately equivalent to a Cohen's d effect size of 1.0, which is considered a large effect.^[53] Because our follow-up is 90 days, we can expect that our effect size will be somewhat lower. Other self-regulation interventions yielded smaller effects over varying timeframes (e.g., $d=0.28-0.78$).^[7] Thus, powering the study to detect an effect of $d=0.30$ of the intervention on behavior (Mental

Imagery Hypothesis 5) would be conservative and reasonable. Based on a 2-sided test of means for 2 groups (t-test) at 80% power, $\alpha=.05$, and Cohen's d effect size of 0.30,^[51, 52] we anticipate needing 352 participants at 90-day follow-up. To account for the possibility of 30% attrition rate due to our underserved sample (unpublished data), we expect needing to enroll 500 participants at baseline to achieve this goal.

Study Procedure Calendar

	Year 1				Year 2				Year 3				Year 4			
	1	2	3	4	1	2	3	4	1	2	3	4	1	2	3	4
Startup (hiring, IRB amendments)	X	X	X	X					X							
Biweekly research team meetings	X	X	X	X	X	X	X	X	X	X	X	X	X	X	X	X

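### The 90-day activity analyses (H3, H4 and H5) each leave out the other randomised factor, and no analysis looks at risk presentation by imagery

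*Combined protocol and SAP*

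**What the plan says.** The Design section sets out a "3 (risk presentation condition: text vs. table vs. risk ladder) x 2 (mental imagery condition: physical activity vs. sleep hygiene) experimental design", block randomised so that "each of the 6 experimental conditions has equal numbers of participants at the end of the study".

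In Table 2 (Statistical Considerations, Main Analyses), the H3 test is a "3 arm ANOVA, planned contrast (risk ladder vs. text") on the change in weekly minutes of activity from baseline to 90 days. Its only listed predictor is risk presentation. H4 is a structural equation model of the same outcome, with ladder versus text as predictor and intentions as mediator. H5 is a t-test of the same outcome by imagery condition, and RQ5 adds moderators to it. H6 and RQ6 are confined to the physical activity imagery arm.

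The text before Table 2 allows moderation tests through "interaction terms between the risk presentation condition or mental imagery condition variables, as appropriate, and the variable assessing the moderator of interest". The moderators named in RQ3 and RQ5 are education, race/ethnicity, numeracy, health literacy and graph literacy. Covariates are sex plus personal characteristics picked out in the preliminary analyses. Nothing brings the other randomised factor into any model.

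On theory, the Background says that "the gap between intentions and behavior can be bridged via interventions that help people develop self-regulatory skills". The conceptual model makes entry to the action phase depend on factors outside the motivation phase, and H5 expects activity to rise only under physical activity imagery. H3 itself carries no condition on imagery.

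**The concern.** Imagery starts straight after Baseline Survey 1, and the H3 and H4 outcome is measured 90 days later. By then half of each display arm has been assigned physical activity imagery and half sleep imagery, and the first of these aims at the same outcome. H3 and H4 pool the two halves without a term for the factor that separates them. H5 pools over the three displays in the same way.

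Two things are lost. The smaller is precision: variance from a known, randomised source stays in the error. The larger is interpretation. If a display raises intentions but behaviour follows only when self-regulation support is given, the averaged H3 effect understates what happens in one half and overstates it in the other. The planned output would not reveal this. H4 is where it bears most directly: taking intentions from Baseline Survey 1, imagery comes between the mediator and the outcome and is absent from the model.

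**Working it through.** **Which rows are affected.** Comprehension, intentions, risk perceptions and the affective measures used in H1, H2, RQ2 and RQ3 come from Baseline Survey 1, completed before imagery begins. Imagery cannot have altered them. The 90-day activity outcome is used in H3, H4, H5, RQ5 and H6; of these, H3, H4 and H5 are the between-arm tests at issue.

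**The plan's own figures.** Inputs from Sample Size Calculations: two-sided alpha 0.05, 80% power, d = 0.30, 30% attrition; for the risk calculator, a "2-sided test of means for 3 groups (ANOVA) at 80% power" with Cohen's "f effect size of 0.15".
- Two-group t-test, d = 0.30: 175.4 per arm, so 176 x 2 = 352, as stated.
- Three-group ANOVA, f = 0.15: 431.2, so 432, as stated; 432/0.9 = 480, as stated.
- 352/0.7 = 503, against 500 enrolled (500 x 0.7 = 350 followed up). The gap is immaterial here.

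Both calculations are for main effects. None is given for an interaction.

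**Cell sizes at 90 days.** 352/3 = 117.3 per display arm; 352/6 = 58.7 per cell. Effects below are in within-cell SD units.

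**Precision lost by leaving imagery out of H3.** An omitted 50:50 factor with effect d adds d²/4 to the error variance.
- d = 0.30 (planning value): 0.09/4 = 0.0225, about 2%.
- d = 0.78 (top of the range cited for other self-regulation interventions): 0.6084/4 = 0.152, about 15%.
- Power of the H3 contrast at 0.30 SD, imagery omitted versus included: 62% versus 63% if imagery d = 0.30; 54% versus 63% if imagery d = 1.0 (the plan's conversion of the earlier imagery trial).

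**What the H3 contrast estimates.** With equal cells it is the mean of the two simple effects. The documents give no interaction size, so the following are assumptions, with SE = sqrt(2/117.3) = 0.131:

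| Ladder effect, activity imagery | Ladder effect, sleep imagery | H3 estimates | H3 power |
|---|---|---|---|
| 0.30 | 0.30 | 0.30 | 63% |
| 0.30 | 0.15 | 0.225 | 40% |
| 0.30 | 0 | 0.15 | 21% |

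These rows compare assumed truths, not analyses. Adding the interaction term changes none of them.

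**What an added interaction term could deliver.** The term is the ladder-versus-text difference under activity imagery minus the same difference under sleep imagery.
- SE = sqrt(4/58.7) = 0.261; 95% half-width = 1.96 x 0.261 = 0.51 SD.
- Power: 21% for a difference of 0.30 SD, 63% for 0.60 SD.
- Detectable difference at 80% power: 2.80 x 0.261 = 0.73 SD.
- For 80% power at 0.30 SD: 349 per cell, 349 x 6 = 2,094 followed up, 2,094/0.7 = 2,992 enrolled.
- Ladder versus text within one imagery condition: SE = sqrt(2/58.7) = 0.185, half-width 0.36 SD, 37% power at 0.30 SD.

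**The case against.** The strongest reply is that testing each factor at its margin is a recognised analysis of a balanced factorial. Allocation is equal across cells, so the H3 and H5 contrasts are unbiased for the averaged effects. That stands. A reader might infer from the missing terms that H3 is biased or that the factorial has been wasted; the documents support neither.

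A second reply is that the protocol never hypothesises an interaction. H3 is unconditional, and the Background calls the effect of calculators on behaviour modest, not absent, and speaks of calculators in general, not of ladder against text. That also stands. A differing ladder effect is a plausible inference from the conceptual model read with H5. It is not the plan's own prediction.

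Third, a reader might take 21% against 63% as the power lost through the planned analysis. It is not: the ladder-versus-text contrast remains the H3 test after the fix and would have the same low power if the effect were confined to one imagery condition. The claim that H3 captures only half the effect likewise holds only if the effect under sleep imagery is exactly zero.

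Fourth, H3 and H4 are secondary, H4 is tied to a significant ladder effect on activity, and the gain in precision is slight at the planning effect. This limits the consequence. It does not argue against a change that costs almost nothing, and H5, which is primary, has the same form.

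**Conclusion.** The point holds as a low-cost improvement to the 90-day analyses. No planned model contains both randomised factors, and none examines risk presentation by imagery, so the planned analyses cannot show whether the averaged ladder effect is uniform across imagery conditions. It would go too far to say that the trial cannot show it: data for all six cells will exist. Equally, the added term would not settle the matter at this size, since only differences of about 0.73 SD are detectable with 80% power.

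The cost in precision is about 2% of error variance at d = 0.30 and about 15% at d = 0.78. These figures assume 352 followed up, equal cells after attrition and a common within-cell SD. The 0.30 SD interaction is an assumption, not a figure from the plan.

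**What to change.** In Table 2:
1. **H3 and H5:** fit a linear model with risk presentation and imagery condition as main effects. Keep ladder versus text as the H3 test and the imagery contrast as the H5 test.
2. **H4:** add imagery condition as a predictor of activity change. Letting imagery moderate the path from intentions to activity is optional and should be labelled exploratory.
3. **New exploratory row:** ladder versus text by imagery on 90-day change. Report the interaction with its 95% CI (expected half-width about 0.51 SD), the ladder-versus-text effect in each imagery condition (about 0.36 SD), and all six cell means.
4. **Sample Size Calculations:** state that the trial is not powered for this term (about 21% at an assumed 0.30 SD; detectable difference about 0.73 SD at 80% power), and that it does not decide whether the H3 or H5 main effect is reported.

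The plan falls back on non-parametric tests when ANOVA assumptions fail, so it should also name a fallback that can carry two factors.

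The cost is some wording and a few model terms, with no new data or participants. The downside is an imprecise exploratory estimate that could be over-read, which is why its label and interval should be fixed in advance.

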Baseline Survey 2 (Appendices L and M)	Immediately following completion of the mental imagery activity. The specific item wording is tailored based on which mental imagery condition is assigned (i.e., mental imagery vs. sleep), but the constructs assessed are the same for both conditions.	Message acceptance, ^[41] perceived clarity and vividness of images; ^[5, 9] and the following items obtained, developed, or adapted from: ^[5, 6, 9, 34] action plan; coping plan; action self-efficacy; recovery self-efficacy; and maintenance self-efficacy.
--	--	--

Part 2: Text Messaging

Mid-Intervention Text Message Surveys (Appendices X and Y)	1, 2, 3, and 4 weeks after Part 1	Perceived clarity and vividness of images; ^[5, 9] and the following items obtained, developed, or adapted from: ^[5, 6, 9, 34] action plan; coping plan; action self-efficacy; recovery self-efficacy; and maintenance self-efficacy.
--	-----------------------------------	--

Part 3: 90-Day Follow-Up

Follow-Up (Appendix BB)	90 days after Part 1	Comprehension; ^[31] physical activity behavior, ^[26, 27] sleep behavior, ^[9] tobacco use, ^[27] and the same items as in Baseline Survey 2 assessing intentions, action self-efficacy, cognitive and affective perceived risk, response efficacy, anticipated regret, and affective attitudes.
-------------------------	----------------------	---

Note: Race and education will be assessed during eligibility for recruitment stratification purposes only. Baseline Survey 1 excludes characteristics that will be assessed in the Risk Assessment questionnaire.

Statistical Considerations

Preliminary Analyses

We will begin by using descriptive statistics to understand the frequency and distributional properties of all items. For variables with non-normal distributions, data transformations or non-parametric tests will be used for subsequent analyses.

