Cronbach α will be used to test the internal consistency of multi-item constructs in Baseline Survey 1 (i.e., cognitive and affective perceived risk; response efficacy; action self-efficacy; affective reaction to the information; affective attitude about exercise; anticipated regret; intentions to engage in physical activity, message acceptance), Baseline Survey 2 (i.e., message acceptance, perceived clarity and vividness of images), and the Follow-Up Survey (i.e., intentions, action self-efficacy, cognitive and affective perceived risk, response efficacy, anticipated regret, affective attitude about exercise). Where $\alpha \geq .70$ we will create a scale by averaging responses to a given construct across diseases. That average score will be used in subsequent analyses. Comprehension, numeracy, and graph literacy will each be operationalized as continuous variables comprised of the number of items answered correctly.

Next, we will verify that participant characteristics (i.e., demographics, personal diagnosis of one of the target

diseases, self-reported health status, numeracy, health literacy, graph literacy, pre-intervention minutes of physical activity per week) are equivalent across experimental conditions by conducting t-tests, one-way ANOVAs, chi-square tests, or other tests, as appropriate. If any differences are found, these variables will be included in subsequent analyses as potential covariates. Personal characteristics will also be explored to determine if they are related to the outcomes of interest. Any characteristic that has a significant association with the outcomes will be included in subsequent analyses as potential covariates.

Main Analyses

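### The primary model for H5 (imagery effect on activity) is not fixed in advance: Table 2 names a t-test on change, while the text leaves sex, baseline adjustment and the handling of skew open

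*Combined protocol and SAP*

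**What the plan says.** All references are to the combined protocol and SAP, Statistical Considerations.

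- **Table 2, row H5.** Priority is primary, the test is a t-test, and the predictor is mental imagery condition alone. The outcome is "Change in physical activity (mins/week at 90 days – mins/week at baseline" (the same outcome also appears in the H3, H4, RQ5 and H6 rows). Main Analyses introduces the table with "Table 2 below describes the analyses that will be conducted for each hypothesis or research question".
- **Main Analyses, covariates.** In a paragraph that opens by covering every hypothesis and research question: "Sex will be a covariate because there are no valid prediction models for male breast cancer". Then: "The inclusion of other personal characteristics as covariates will be determined by the results of the preliminary analyses".
- **Preliminary Analyses, covariates.** Pre-intervention minutes per week are among the characteristics compared between conditions: "If any differences are found, these variables will be included in subsequent analyses as potential covariates". A second trigger follows: "Any characteristic that has a significant association with the outcomes will be included in subsequent analyses as potential covariates".
- **Non-normal data.** Preliminary Analyses says "data transformations or non-parametric tests will be used for subsequent analyses". Main Analyses says "If there are violations, non-parametric tests will be used instead". Neither names the transformation or the test.
- **Sample Size Calculations, Mental Imagery.** A two-sided two-group t-test at 80% power, alpha 0.05 and d = 0.30 gives 352 at 90 days. With 30% attrition, 500 are to be enrolled.

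**The concern.** A plain two-sample t-test has no place for a covariate, so the H5 row and the sex rule cannot both be followed literally for H5. The H3 and RQ5 ANOVAs do not meet this difficulty. Baseline minutes can enter as a regressor only if a balance or association test comes out significant, and then only as a potential covariate, with no rule for when potential becomes actual. If minutes are skewed, a transformation or an unspecified non-parametric test may take over, and a simple two-group rank test holds neither sex nor baseline.

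At least four primary analyses therefore fit the text: a bare t-test, a linear model with sex, a linear model with sex and baseline, and a rank test. What is at stake is that the trial's primary behaviour result would rest on a model settled after the data are seen, although a single model could be named now from data already being collected.

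**Working it through.** **1. Reproduce the plan's figure.** Inputs from Sample Size Calculations: d = 0.30, two-sided alpha 0.05, 80% power, equal arms.
- Non-central t: 175.4 per arm, so 176 per arm and 352 in total, as stated. Power is 80.1% (non-centrality 0.30 × √(176/2) = 2.814, 350 df).
- Attrition: 352/0.70 = 502.9, so 503 against the stated 500. With 500 enrolled, 500 × 0.70 = 350 completers and power is 79.9%. The shortfall is immaterial.

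**2. Baseline-adjusted model against the change-score t-test.** Let k = SD at baseline / SD at 90 days, and r = their correlation. Both are assumptions. In units of the 90-day variance:
- variance of change = 1 + k² − 2rk
- residual variance after adjustment = 1 − r²
- ratio VR = (1 + k² − 2rk)/(1 − r²) = 1 + (k − r)²/(1 − r²)

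So the gain is zero exactly when r = k, which is when the slope of 90-day on baseline minutes, r/k, equals 1. The effective d is 0.30 × √VR. To charge for estimating p covariates, the variance is multiplied by (N − 3)/(N − 3 − p). With a cautious p = 4 (baseline, sex and two presentation terms), this is 349/345 = 1.0116, with 346 df. Power at 352:

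| k | r | VR | Power |
|---|---|---|---|
| 0.3 | 0.2 | 1.010 | 80.1% |
| 0.3 | 0.5 | 1.053 | 81.7% |
| 0.4 | 0.3 | 1.011 | 80.1% |
| 0.5 | 0.2 | 1.094 | 83.1% |
| r = k | r = k | 1.000 | 79.7% |
| 0.6 | 0.3 | 1.099 | 83.3% |
| 0.6 | 0.5 | 1.013 | 80.2% |
| 0.8 | 0.3 | 1.275 | 88.3% |
| 1.0 | 0.5 | 1.333 | 89.7% |

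The worst case, r = k, costs 80.1 − 79.7 = 0.4 points. With only baseline and sex (349/347 = 1.0058, 348 df) the same case gives 79.9%, a loss of 0.2.

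**3. Which k is plausible.** Eligibility requires under 150 minutes per week. On a 0-150 range the SD cannot exceed 75, and is 150/√12 = 43.3 if uniform. k = 1 would need a 90-day SD no larger than the baseline SD. If the analysed baseline obeys the entry cut-off, the lower k values are the more likely ones. The documents do not say which pre-intervention measurement is analysed, so this is a guide and not a bound.

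**4. Adjusted model against the preliminary-test rule.** Simulation: 6,000 trials per setting, 352 completers, normal data. The rule adds baseline if the balance or the association test has p < 0.05, then fits a linear model of change with sex.

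| k, r | Rule power | Adjusted power | Baseline enters |
|---|---|---|---|
| 0.4, 0.3 | 79.7% | 79.6% | 52.6% |
| 0.5, 0.2 | 82.4% | 82.1% | 100% |
| 0.5, 0.5 | 79.9% | 79.5% | 9.8% |
| 0.6, 0.3 | 83.4% | 83.1% | 100% |
| 0.6, 0.5 | 80.9% | 80.7% | 58.9% |
| 0.8, 0.3 | 88.4% | 88.1% | 100% |
| 1.0, 0.5 | 89.3% | 89.2% | 100% |

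There is no power gain over the rule. Type I error is 4.6-5.6% for the rule and 4.6-5.4% for the adjusted model. The simulation screens baseline minutes only, not every characteristic on the plan's list, and does not exercise the skew route.

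**5. Does the choice of model matter?** In a second simulation of the same size at d = 0.30, the bare t-test and the model with baseline and sex disagree on significance in about 12.5% of trials at k = 1, r = 0.5, about 5% at k = 0.5, r = 0.3, and about 1.6% at k = r = 0.5.

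**The case against.** The best defence is that the conflict is largely one of format. Table 2 is an overview with no covariate column, and no row lists sex, not even H1, so its absence from the H5 row shows little. A two-group t-test is the same linear model as a two-group ANOVA, and a statistician would read the covariate text as extending it. The reason given for sex concerns the breast cancer display in the risk calculator, so the rule may never have been meant for the imagery test. Every participant's baseline is already subtracted. All of this stands, and it reduces the contradiction to an ambiguity. It does not remove the ambiguity: the plan nowhere says whether sex applies to H5, when a potential covariate becomes an actual one, or which route skewed minutes take.

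A reader might infer more. One inference is that the t-test on change is biased or underpowered. It is neither: randomisation protects it, and the 352 reproduces. Another is that the trial gives up substantial power. The larger gains in the working need k near 1, which the entry criterion makes less likely. A third is that type I error is inflated. Each single analysis stays near 5%. Only reporting the better of the t-test and the adjusted model raises it, to about 5-7% over three assumed settings, and nothing in the documents suggests that this is intended.

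**Conclusion.** The point holds as a minor matter of pre-specification. The primary H5 analysis is not uniquely defined with respect to sex, baseline minutes and skewed data, and a few sentences would define it. The main benefit is removing a data-driven choice of primary model. Extra precision over the bare t-test is possible but cannot be promised, because it rests on assumed k and r and on normal data.

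Baseline adjustment alone would not settle everything. The covariate-selection rule and the skew route must be closed for H5 as well. List-wise deletion with 30% expected attrition is a separate matter that this change does not touch.

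**What to change.** In Table 2 (row H5) and Main Analyses:

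1. Name one primary H5 model: a linear model of 90-day minutes on imagery condition, with baseline minutes always included whatever the preliminary tests show.
2. State whether sex is in that model.
3. State that no other covariate enters the primary H5 model because of the preliminary balance or association tests. Any model built that way is a sensitivity analysis.
4. Replace the open choice between a transformation and a non-parametric test with one named approach for H5. One option is to keep this model with heteroscedasticity-robust standard errors and add a named rank-based sensitivity analysis. Robust standard errors deal with unequal variance and not with skew as such, which is why the second analysis is useful.
5. State that H5 is judged on the between-arm imagery coefficient.

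Risk-presentation condition may be added, but nothing in the plan requires it for H5.

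The cost is wording only. Physical activity is already collected before randomisation and at 90 days. The model uses a few degrees of freedom, at worst about 0.4 power points. The sample size of 352 completers and 500 enrolled can stay.
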